Compared to a 50g glucose control, Thondre et al. showed that there was a dose response effect of pea protein (25g and 50g) on postprandial glycaemia and stimulated insulin release over a three hour period in healthy adults (14).

RANDOMISATION AND BLINDING

The study will be a four-visit, single-blind, acute crossover study; with at least a one week washout period between visits. A computer-generated randomisation scheme will be prepared by a statistician who is independent of the study team and provided to the researcher who is preparing the test beverages (CK).

The researcher will prepare beverages for each visit for each participant according to the randomisation list. To maintain participant blinding, beverages will be provided in identical opaque containers labelled with the participant number and the intervention period. Thus, the participants will be unaware which beverage they are taking during each visit.

PROPOSED OUTCOMES

Primary endpoint: Circulating concentrations of intact GLP-1 in blood.

Secondary endpoints: Circulating concentrations of other satiety hormones, glucose and insulin concentration, amino acid availability in blood.

Exploratory endpoints: Metabolomic and proteomic markers in blood.

SAMPLE SIZE

Based on variability data from previously published studies in similar populations (6, 8), as well as unpublished data from our own group, a sample size of 16 participants will give the study 80% power to detect a significant difference of 10-15% in total AUC GLP-1 between treatment conditions (WP vs FB; or WPG vs FPG) or a difference in AUC Glucose of 5-15% between treatment conditions (WPG vs FPG).

To allow for dropout, it is anticipated that 20 participants will be recruited.

STUDY ASSESSMENTS

All assessments will be carried out at the Northern Ireland Clinical Research Facility, U Floor, Belfast City Hospital tower block.

Questionnaires (paper copies provided for completion):

All participants will be asked to complete a short lifestyle questionnaire (sex, age, food and drinks, alcohol, physical activity and smoking status (adapted from Leeds Short Form Food Frequency Questionnaire (20)); see Appendix 8.0) at their first visit.

Visual analogue scales (see Appendix 9.0) to rate feelings of hunger will be completed during each study visit at T0 (before the drink is consumed), T30, T60, T90 and T120 (minutes).

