Primary and secondary endpoints will be analysed using repeated measures ANOVA (for normally distributed data) and non-parametric Friedman test (where data were not normally distributed) to compare concentrations at each time point. Incremental Area under the Curve (iAUC) (at 30, 60, 90 and 120 min) will be calculated and reported along with peak concentration and time of peak concentration for relevant endpoints in response to each of the interventions. Post hoc analyses will be performed using the Bonferroni correction for parametric data and the Wilcoxon signed-rank test for non-parametric data. Statistical significance will be set at p value ≤ 0.05 for all tests.

Metabolomic and proteomic analysis will be considered exploratory analysis. P-values will not be altered for multiple testing, but findings will be treated as hypothesis generating rather than hypothesis testing.

PROPOSED TIMELINE FOR THE STUDY

January – February 2024 – Obtain ethical approval; study set-up

February – March 2024 – Recruitment

February – June 2024 – Completion of dietary interventions

July-December 2024 – Laboratory analysis, statistical data analysis and write-up

STUDY PHONE NUMBER AND EMAIL ADDRESS

To ensure personal telephone numbers are not given out we have obtained a mobile phone unique to the study.

Contact information for study participants:

Email address: [contact] or [contact]

[contact]

ETHICAL CONSIDERATIONS

The study will be carried out in accordance with the declaration of Helsinki. Ethical approval will be obtained from the Faculty of Medicine, Health and Life Sciences Research Ethics Committee at Queen's University Belfast. Participants will be given full details of the study and will have the opportunity to ask questions. All participants will provide written informed consent prior to participation and will be informed that they can withdraw from the study at any time without having to give a reason. Participants will be informed that any data or samples provided up to the point of withdrawal may be included in the study unless they request otherwise. Participants can also request withdrawal of their data or samples at any time after completion of the study by contacting the Chief Investigator; any data or samples that have been analysed or reported at the time of request will not be able to be retracted.

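### The 80% power is stated for total AUC of GLP-1, a quantity that the analysis section never analyses

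*Protocol*

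**What the plan says.** Three sections of the protocol bear on the primary GLP-1 result.

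- **Proposed Outcomes** names the measured variable but no summary of it: "Primary endpoint: Circulating concentrations of intact GLP-1 in blood".
- **Sample Size** rests on one particular summary. It claims "80% power to detect a significant difference of 10-15% in total AUC GLP-1", for WP vs FP or for WPG vs FPG. It adds "a difference in AUC Glucose of 5-15% between treatment conditions (WPG vs FPG"), without saying whether that AUC is total or incremental. The variability is attributed to cited studies and unpublished data; no SD is given.
- **Statistical Analysis** applies repeated measures ANOVA, or Friedman if the data are not normal, to the primary and secondary endpoints "to compare concentrations at each time point". It then says "Incremental Area under the Curve (iAUC) (at 30, 60, 90 and 120 min) will be calculated and reported", together with peak and time of peak. Post hoc comparisons use Bonferroni for parametric data and Wilcoxon signed-rank tests otherwise. The 0.05 level applies to every test.

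Total AUC is not named as an endpoint or as an analysed quantity. Outside the sample-size statement, it is mentioned only where the Dosage section describes a cited soya and whey study.

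**The concern.** A power statement belongs to one variable and one test. Here it belongs to total AUC, while the analysis is fixed on other quantities. Total AUC averages all five samples, including the fasting one. A single time point uses one sample. Incremental AUC subtracts the fasting area. These have different variances, and the same percentage means different things on each. If, say, the fasting area were half of the total, 10-15% of total AUC would be 20-30% of iAUC.

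Two things are at stake. The investigators cannot say what power the planned primary analysis has. And since no single variable is named as primary, the protocol does not say which GLP-1 result answers the question: one time point, several, or a summary. In the non-parametric branch the pairwise Wilcoxon tests also carry no stated correction.

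**Working it through.** **Inputs from the protocol.** n = 16; power 80%; difference 10-15% of total GLP-1 AUC; alpha 0.05; samples at 0, 30, 60, 90 and 120 minutes; each participant takes all four beverages, so comparisons are paired.

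**Assumptions, not in the protocol.** Two-sided test; paired differences with equal variance at the five times and a common correlation ρ between them; a constant difference after the drink and none at T0; iAUC taken as net (the whole fasting area subtracted).

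**1. The protocol's own figure.** It can be neither reproduced nor refuted without an SD. Working backwards, a paired t test with 15 degrees of freedom (noncentral t) has 80% power when the standardised difference is d = 0.749. The implied SD of the paired difference is 10/0.749 = 13.3% of the mean for a 10% difference, and 15/0.749 = 20.0% for 15%.

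**2. Variances.** A weighted sum of the five values with weights a has variance proportional to (1−ρ)Σa² + ρ(Σa)².

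- Total AUC (trapezoid, divided by 120): a = (1,2,2,2,1)/8, so Σa² = 14/64 and Σa = 1. Variance 0.219(1−ρ) + ρ.
- Net iAUC: a = (−7,2,2,2,1)/8, so Σa² = 62/64 and Σa = 0. Variance 0.969(1−ρ).
- Single time point: variance 1.
- Mean of five times (ANOVA treatment main effect): variance 0.2(1−ρ) + ρ.
- Total AUC with T0 as covariate: total-AUC variance minus the squared covariance with T0, where that covariance is 0.125(1−ρ) + ρ.

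**3. Carrying the 80% over.** A difference of one unit at every post-drink time shifts total AUC and iAUC by 7/8, a single post-drink time by 1 and the five-time mean by 4/5. The standardised difference for each variable is

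d = 0.749 × (its shift ÷ 7/8) × √(total-AUC variance ÷ its variance).

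Example at ρ = 0.3, where the total-AUC variance is 0.219 × 0.7 + 0.3 = 0.453:

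- Net iAUC: variance 0.969 × 0.7 = 0.678; d = 0.749 × √(0.453/0.678) = 0.613; power 63%.
- Single time: d = 0.749 × (8/7) × √0.453 = 0.577; power 58%, or 33% at 0.05/4.
- Main effect: variance 0.2 × 0.7 + 0.3 = 0.44; d = 0.749 × (0.8/0.875) × √(0.453/0.44) = 0.695; power 74%.
- Total AUC with T0 covariate: variance 0.453 − 0.3875² = 0.303; d = 0.749 × √(0.453/0.303) = 0.917; power 93% with 14 degrees of freedom.

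| Variable | ρ = 0 | 0.3 | 0.5 | 0.7 |
|---|---|---|---|---|
| Total AUC (set) | 80% | 80% | 80% | 80% |
| Single time, unadjusted | 32% | 58% | 71% | 80% |
| Single time, Bonferroni over 4 times | 15% | 33% | 46% | 57% |
| Net iAUC | 27% | 63% | 88% | 99.5% |
| ANOVA treatment main effect | 76% | 74% | 73% | 73% |
| Total AUC with T0 covariate | 82% | 93% | 98% | >99% |

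Only the first row is what the protocol sized. The row closest to the comparison it describes is the single-time row, with or without a correction.

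**The case against.** The strongest reply is that the two sections are closer than they look. With five equally spaced samples, total AUC is a weighted mean of the concentrations, and a repeated measures ANOVA treatment effect is nearly the same quantity, with 73-76% power against 80%. That is correct, so it would be wrong to say that the power claim is unrelated to the plan. But the protocol states comparison at each time point and does not name that main effect as the primary test. Nor is this a gap that an SAP can simply fill: the protocol fixes one quantity for power and others for analysis, and an SAP would have to override one of them. It is fair to add that naming concentrations as the endpoint is compatible with any summary of them; the conflict lies between the sample-size and analysis sections.

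Some stronger readings are tempting but not supported.

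- **That iAUC is tested.** The text says only that it is calculated and reported. The four times listed may be four windows or just the sampling points used.
- **That power is lower than 80%.** Net iAUC gains power over total AUC at correlations of 0.5 and above. The direction is unknown.
- **That the plan as a whole has a 22-33% chance of a false positive.** That range describes eight Wilcoxon tests (four times, two pairs) with no omnibus step and no correction. The protocol has an omnibus test first and Bonferroni in the parametric branch. What stands is narrower: the Wilcoxon branch states no correction.
- **That the protocol expects ghrelin or glucose to fall below baseline, making iAUC unsuitable.** The Dosage section reports a cited infusion study in which they were lower than with saline. That is neither a comparison with baseline nor an expectation for this trial.

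**Conclusion.** The mismatch is real and follows from the text alone: the trial is sized on total GLP-1 AUC, and its analysis section never analyses total AUC. The 80% does not carry over to the stated analysis.

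How far off it is cannot be determined. With total AUC held at 80%, power ranges from 15% for a single time point with Bonferroni over four times at zero correlation to over 99% for net iAUC at 0.7. These figures rest on an assumed equal-correlation structure, a constant post-drink difference, two-sided testing and net iAUC; none of these is in the documents. They show that the 80% does not transfer; they do not estimate the trial's power. The lack of a single deciding variable needs no assumption.

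**What to change.** Name one primary GLP-1 variable and use it in the Proposed Outcomes, Sample Size and Statistical Analysis sections. The natural choice is the quantity the trial is sized on: total AUC from 0 to 120 minutes by the trapezoid rule, compared within each pair (WP vs FP; WPG vs FPG), with that visit's T0 value as covariate. In the illustration above this has 82% to over 99% power, never below the alternatives. Make time-point comparisons, iAUC, peak and time of peak secondary, and state a correction for Wilcoxon tests where they remain.

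If time points or iAUC are to stay primary, restate the power for that quantity. Either way, the power statement should give the SD, a single effect size, the sidedness and any adjustment for multiple comparisons.

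The cost is wording only, since T0 is already sampled at every visit. The downside is that time-point results lose primary status and the covariate uses one degree of freedom. Log transformation, and the same summary for other analytes, are optional and not needed to cure the mismatch.
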